4. EFFICACY

A validated computerized algorithm, which is based on the IMWG response criteria (Durie 2006, Rajkumar 2011)^{1, 2} and has been used and validated by an independent review committee (IRC) in Study MMY2002, will be used to determine response and disease progression for each subject. As a sensitivity analysis, investigator assessment of response and disease progression using the IMWG response criteria will also be performed.

4.1. Analysis Specifications

4.1.1. Level of Significance

All statistical hypothesis tests and 95% confidence interval presented will be 2-sided.

The primary hypothesis is to be tested at the 0.05 significance level (overall). The exact significance level at the second interim analysis is to be determined by the observed number of events per the O'Brien-Fleming alpha spending function. Assuming 234 PFS events are observed at the second interim analysis, the alpha to be spent will be 0.0076 (2-sided) for the interim analysis and 0.0476 (2-sided) for the primary PFS analysis (390 PFS events occur). If the observed two-sided p-value is smaller than this significance level as specified above, the superiority of DRd versus Rd with respect to PFS will be established.

If the primary endpoint of PFS is statistically significant, the following secondary endpoints ordered below will be sequentially tested, each with an overall two-sided alpha of 0.05, by utilizing a hierarchical testing approach as proposed by Tang and Geller (1999) that strongly controls Type I error rate:

- 1) CR or better rate
- 2) VGPR or better rate
- 3) MRD negativity rate (10⁻⁵)
- 4) Overall response rate (ORR)
- 5) Overall survival (OS)

These secondary endpoints will be tested at the 2nd IA and the primary PFS analysis. The primary PFS analysis will be skipped if PFS is positive at the 2nd IA. If this is the case, the protocol will be amended to add an analysis for secondary endpoints at a similar timing as the planned primary PFS analysis (note that OS will also be tested at its protocol-specified final analysis). The significance level at the second interim and the primary PFS analyses will be determined by the alpha-spending function specific to endpoints:

- For ORR, VGPR or better rate, CR or better rate, and MRD negativity rate (10⁻⁵), the information fraction is expected to be 80% at the 2nd IA. The O'Brien-Fleming alphaspending function as implemented by the Lan-DeMets method will be used for alphaspending: 0.0244 (two-sided) at the 2nd IA and 0.0428 (two-sided) at the primary PFS analysis.
- For OS, a modified linear alpha spending function will be used to determine the alpha level at three looks (2nd IA, primary PFS analysis, and final OS analysis). The alpha level will be 0.0001 for the first OS look, and linear spending function will be used to determine the alpha level for the second and last looks. For example, if 59% targeted OS events are observed at the second look, the corresponding alpha level will be 0.0295.

If the null hypothesis for any of these endpoint fails to be rejected at the second interim analysis, then any subsequent endpoint(s) listed above will not be tested until the next analysis time point (e.g., primary PFS analysis), if applicable. If the null hypothesis for an endpoint is rejected at the

second interim analysis, it will remain being rejected and will not be re-tested at any subsequent time points, if any.

4.1.2. Data Handling Rules

There is no imputation planned for missing efficacy endpoint values.

4.2. Primary Efficacy Endpoint

The primary efficacy endpoint is progression-free survival (PFS) based on the computerized algorithm.

4.2.1. Definition

PFS is defined as the duration from the date of randomization to either progressive disease, according to the IMWG response criteria, or death, whichever occurs first. Subjects who start subsequent antimyeloma therapies for multiple myeloma without disease progression will be censored at the last disease assessment before the start of subsequent therapies. Subjects who withdrew consent from the study before disease progression will be censored at the last disease assessment before withdrawal of consent to study. Subjects who are lost to follow-up will be censored at the last disease assessment before subjects are lost to follow-up. Subjects who have not progressed and are still alive at the cutoff date for analysis will be censored at the last disease assessment. Subjects without any post-baseline disease assessment will be censored at the randomization.

Determination of dates of PFS event and dates for censoring is summarized in Table 2 as follows.

Table 2: PFS Event and Censoring Method

Situation	Date of Progression or Censoring	Outcome
Disease progression prior to start of	Earliest date that indicates disease progression	PFS event
subsequent antimyeloma therapy		
Death without subsequent antimyeloma	Date of death	PFS event
therapy		
No post-baseline disease assessment	Randomization	Censored
Other (e.g., withdrawal of consent to study	Date of last disease assessment prior to	Censored
participation, lost to follow-up, start of subsequent	withdrawal of consent to study participation, lost to	
antimyeloma therapy etc.)	follow-up, or subsequent antimyeloma treatment	
/	- · · ·	

4.2.2. Analysis Methods

Analysis of PFS will be based on the ITT population. The Kaplan-Meier method will be used to estimate the distribution of overall PFS for each treatment group. The median PFS with 95% CI will be provided. In addition, the number and percentage of subjects who had a PFS event or were censored will be reported. The Kaplan-Meier PFS curve will also be plotted by treatment group.

The primary treatment comparison of the distribution of overall PFS will be based on a stratified log-rank test. The p-value from a stratified log-rank test will be reported. Hazard ratio and its 95% confidence interval will be estimated based on a stratified Cox's regression model with treatment as the sole explanatory variable. Stratification factors used in the analyses include ISS staging (I, II, III), region (North America vs other), and age (<75 years vs ≥75 years).

In addition, 12, 24 and 36-months of PFS rate with 95% CI will be estimated by Kaplan-Meier method and reported for each treatment group.

Additionally, reasons for PFS event and censoring will be summarized for ITT population.

4.2.3. Sensitivity Analysis of PFS

The following sensitivity analysis is planned to evaluate the robustness of the primary endpoint analysis of PFS.

4.2.3.1. Progressive Disease Based on Investigator Assessment

A sensitivity analysis of PFS, in which progressive disease is based on investigator assessment according to the IMWG response criteria, will be performed in a similar manner as described in the Section 4.2.2.

The PFS definition used in the sensitivity analysis is similar to that defined in the Section 4.1.2, except for date of progressive disease and date of censoring. The date of progressive disease is the date of initial disease progression recorded in the Disease Progression CRF page or earliest date of confirmed progressive disease recorded in the Evaluation of Response CRF page, based on investigator assessment. Similarly, the censoring date is the latest date of disease response recorded in the Evaluation of Response CRF page, based on investigator assessment.

In addition, reasons for PFS and censoring based on investigator assessment will be summarized for ITT population.

4.2.3.2. Not Censored for Start of Subsequent Anticancer Therapies

A sensitivity analysis of PFS derived from the algorithm by not censoring data due to start of subsequent anticancer therapies for subjects, who have not developed a confirmed progressive disease, will be performed in a similar manner as described in Section 4.2.2.

The PFS definition used in the sensitivity analysis is similar to that defined in Section 4.2.1, except for censoring data due to start of subsequent anticancer therapies. Subjects who start subsequent anticancer therapies for multiple myeloma without disease progression will NOT be censored at the last disease assessment before the start of subsequent therapies. If there is no confirmed progressive disease, the subjects will be censored at the last disease assessment before subjects are lost to follow-up or withdrawal of consent to study.

Determination of dates of PFS event and dates for censoring is summarized in Table 3 as follows

Table 3: PFS Event and Censoring Method

Situation	Date of Progression or Censoring	Outcome
Disease progression	Earliest date that indicates disease progression	PFS event
Death	Date of death	PFS event
No post-baseline disease assessment	Randomization	Censored
Other (e.g., withdrawal of consent to study participation, lost to follow-up, start of subsequent anticancer therapy etc.)	Date of last disease assessment	Censored

4.2.3.3. Censored for Death/PD after Missing More Than One Disease Evaluation

A sensitivity analysis of PFS derived from the algorithm by censoring for death or progression after missing consecutive evaluations will be performed in a similar manner as described in Section 4.2.2

The PFS definition used in the sensitivity analysis is similar to that defined in Section 4.2.1, except for death or progression after missing more than one disease evaluation. For any PFS (death or progression) event identified by the computer algorithm, if the event date and the latest date of scheduled disease evaluation (includes serum M-protein, urine M-protein, serum FLC and corrected calcium only) immediately preceding the event differs more than 2.5 disease evaluation intervals, which indicates that subject missed at least one scheduled disease evaluation, then this event will not be considered as a PFS event in the sensitivity analysis. Instead, the subject will be censored at the date of last disease evaluation (includes serum M-protein, urine M-protein, serum FLC and corrected calcium only) prior to the PFS event originally identified.

4.2.3.4. Per-protocol Analysis of PFS

A sensitivity analysis of PFS derived from the algorithm based on Per-protocol population will be performed in a similar manner as described in Section 4.2.2.

4.2.3.5. Unstratified Analysis of PFS

A sensitivity analysis of PFS by using unstratified log-rank test and unstratified Cox's regression model will be performed in a similar manner as described in Section 4.2.2.

4.3. Secondary Endpoints

Secondary efficacy endpoints include overall response rate (ORR), VGPR or better rate, CR or better rate, MRD negativity rate, OS, TTP, PFS2, sCR rate, time to subsequent antimyeloma treatment, time to response and duration of response.

4.3.1. CR or Better Rate

4.3.1.1. **Definition**

CR or better rate is defined as the proportion of subjects with a response of CR or better (i.e., CR or sCR) based on the computerized algorithm, according to IMWG response criteria, during or after the study treatment.

4.3.1.2. Analysis Methods

CR or better rate will be calculated for each treatment group based on the ITT and response-evaluable population. The number and percentage of subjects in the following response categories will be presented by treatment group: stringent complete response (sCR), complete response (CR), sCR+CR, very good partial response (VGPR), VGPR or better (sCR+CR+VGPR), partial response (PR), overall response (sCR+CR+VGPR+PR), stable disease (SD), progressive disease (PD), and not evaluable (NE). The corresponding 95% exact CI will be provided.

Stratified CMH test will be used to test treatment difference in ORR, VGPR or better rate, CR or better rate and sCR rate. The CMH estimate of odds ratio and its 95% confidence interval and p-value for testing treatment difference will be reported. Stratification factors used in the analysis include ISS staging (I, II, III), region (North America vs. Other), and age (<75 years vs. ≥75 years).

A sensitivity analysis, which disease response is based on investigator assessment according to the IMWG response criteria, will be performed in a similar manner as described above.

4.3.2. VGPR or Better Rate

4.3.2.1. Definition

VGPR or better rate is defined as the proportion of subjects with a response of VGPR or better (i.e., VGPR, CR or sCR) based on the computerized algorithm, according to IMWG response criteria, during or after the study treatment.

4.3.2.2. Analysis Methods

Similar statistical methods will be applied as described in Section 4.3.1.2for CR or better rate analysis.

4.3.3. MRD Negativity Rate

For this study, three threshold values, 10^{-4} , 10^{-5} and 10^{-6} , will be used to evaluate MRD negativity status and its predictive value for PFS.

4.3.3.1. Definition

MRD negativity rate is defined as the proportion of subjects who have negative MRD at any time point after the date of randomization and prior to subsequent antimyeloma therapy. MRD

positive subjects include subjects of which all tested results were found to be MRD positive, or indeterminate, or unavailable (calibration failure or missing).

4.3.3.2. Analysis Methods

The MRD negativity rate will be calculated for each treatment group based on the ITT population. The corresponding 95% exact CI will be provided.

For each threshold value, Fisher's exact test will be used to test if the MRD negativity rate is the same between the two treatment groups in the previously untreated myeloma setting.

For the purpose of hierarchical testing (Section 4.1.1), the threshold value of 10⁻⁵ will be employed using ITT populations.

The durability of MRD negativity may be examined for each treatment group by the proportion of subjects remaining MRD negative 12 months after initial MRD negativity if data becomes available.

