11. STATISTICAL METHODS

Statistical analysis will be done by the sponsor or under the authority of the sponsor. A general description of the statistical methods to be used to analyze the efficacy and safety data is outlined below. Specific details will be provided in the Statistical Analysis Plan.

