11.3. Efficacy Analyses

Response to study treatment and progressive disease will be evaluated by a validated computer algorithm.

Primary Endpoint

For the primary endpoint of PFS, the primary analysis will consist of a stratified log rank test for the comparison of the PFS distribution between the 2 treatment arms. The Kaplan-Meier method will be used to estimate the distribution of overall PFS for each treatment. The treatment effect (hazard ratio) and its two-sided 95% confidence intervals are to be estimated using a stratified Cox regression model with treatment as the sole explanatory variable.

Secondary Endpoints

Other time-to-event efficacy endpoints, including TTP, PFS2, OS, and time to subsequent anti myeloma treatment, will be analyzed using the same method as for PFS. For overall survival, the final analysis will occur after approximately 390 deaths have been observed. Earlier analyses, in which overall survival is analyzed, will be considered as interim analyses. Even though the significance of PFS has already been established at the second interim analysis, testing of OS will continue as planned until a definitive conclusion on OS is reached. The details about testing of OS over time are specified in Section 11.10. The analysis of OS may be confounded by subjects from Arm A receiving daratumumab after disease progression. Exploratory analysis may be performed to adjust for the effect daratumumab exposure may have on OS for the subjects who were randomized to Arm A (Rd).

Comparison between the 2 treatment arms of overall response rates, VGPR or better rate, CR or better rate, and other binary endpoints will be conducted using the stratified Cochran Mantel Haenszel test. The Mantel-Haenszel odds ratio will be provided along with its two-sided 95% confidence interval, and will be provided as the measure of treatment effect. Duration of response will be provided descriptively without formal statistical comparison.

Strong control of familywise Type I error rate will be controlled at a two-sided significance level of 0.05 for the following major secondary endpoints: TTP, CR rate, MRD negativity rate, PFS2 and OS. A sequential hierarchical testing procedure will be used. Details about this hierarchical procedure will be specified in the statistical analysis plan for this study prior to any efficacy analysis.

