1. INTRODUCTION

This statistical analysis plan (SAP) contains definitions of analysis sets, derived variables, and statistical methods for the planned analyses as specified in the protocol JNJ-54767414MMY3008, Amendment INT-4.

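### SAP 4.3.3.2 tests MRD negativity, step 3 of the alpha-controlled hierarchy, with unstratified Fisher's exact test and gives no between-arm estimate; the other response rates get stratified CMH with an odds ratio, and no reason is stated

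*SAP*

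**What the plan says.** SAP 4.1.1 lists five secondary endpoints to be tested in order once PFS is significant: CR or better, VGPR or better, MRD negativity at 10⁻⁵, overall response, and overall survival. The four binary endpoints share a nominal level of "0.0244 (two-sided) at the 2nd IA".

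SAP 4.3.3.2 states that, for each MRD threshold, Fisher's "exact test will be used to test if the MRD negativity rate is the same between the two treatment groups". It names no stratification factors. For estimation it gives the rate in each arm with an exact 95% interval. It then fixes 10⁻⁵ and the ITT population for the hierarchy.

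SAP 4.3.1.2 treats the other response rates differently: "Stratified CMH test will be used to test treatment difference in ORR, VGPR or better rate, CR or better rate and sCR rate". That section also reports a CMH odds ratio with its 95% interval, stratified by ISS, region and age. VGPR or better and overall response refer back to it.

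Section 11.3 of the supplied protocol (Amendment 9) says that comparisons of the response rates "and other binary endpoints will be conducted using the stratified Cochran Mantel Haenszel test". It continues: "The Mantel-Haenszel odds ratio will be provided along with its two-sided 95% confidence interval", as the measure of treatment effect. The same section places MRD negativity among the endpoints with familywise error control, the "major secondary endpoints: TTP, CR rate, MRD negativity rate, PFS2 and OS".

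**The concern.** Randomisation is stratified by ISS, region and age, and the analyses of PFS and the response rates follow those strata. MRD negativity is the only binary endpoint in the hierarchy that does not. The SAP gives no reason here, although it does give one where it leaves overall survival unstratified at the second interim.

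Three things are at stake:

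- **Conservatism.** Fisher's test on a single 2×2 table rejects less often than its nominal level allows, so some of the alpha assigned to this step goes unused.
- **Efficiency.** Ignoring prognostic strata that were balanced by design loses some further power.
- **Estimation.** Two per-arm rates with separate exact intervals do not give a between-arm effect with an interval, so 4.3.3.2 leaves the ITT comparison with a p-value and no effect measure beside it.

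**Working it through.** **The plan's own figure.** SAP 4.1.1 gives an overall two-sided alpha of 0.05, an information fraction t = 0.80 and O'Brien-Fleming-type Lan-DeMets spending. The level is 4 × {1 − Φ[z(1 − 0.05/4)/√t]}. Here z(0.9875) = 2.2414, 2.2414/√0.80 = 2.506, and 4 × 0.006106 = 0.0244. This agrees with the SAP.

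**Inputs.** From the documents: about 730 subjects, 365 per arm, 1:1 allocation, and 3 × 2 × 2 = 12 strata. MRD rates appear in neither document, so all rates below are assumptions.

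**Size and power without strata.** For 365 per arm, the rejection probability is the sum over all outcome pairs (x, y) of Bin(x; 365, p₁) × Bin(y; 365, p₂) × 1[p-value ≤ 0.0244]. This is exact.

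With equal true rates of 5%, 10% and 15%, Fisher's size is 1.54%, 1.80% and 1.87%. The uncorrected chi-square test has 2.43%, 2.43% and 2.45%.

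| Rd v DRd (assumed) | Fisher power | Chi-square power | Loss (points) |
|---|---|---|---|
| 5% v 10% | 58.46% | 63.29% | 4.8 |
| 10% v 20% | 93.03% | 94.35% | 1.3 |
| 20% v 30% | 78.70% | 81.09% | 2.4 |
| 5% v 15% | 98.88% | 99.18% | 0.3 |
| 7% v 24% | 100.0% | 100.0% | 0.0 |

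**Power against stratified CMH.** This was simulated with 20,000 trials per scenario at 0.0244, with CMH uncorrected for continuity, a common odds ratio and equal arms within each stratum. Assumed stratum shares: ISS 27/43/30%, North America 27%, age 75 or over 44%. Assumed log-odds effects: ISS +0.4/0/−0.5, region +0.1/0, age +0.3/−0.3.

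| Rd rate, odds ratio (DRd rate) | CMH power | Fisher power | Loss (points) |
|---|---|---|---|
| 5%, 2.0 (9.4%) | 53.5% | 48.0% | 5.5 |
| 7%, 2.0 (13.0%) | 68.2% | 63.2% | 5.0 |
| 10%, 1.8 (16.5%) | 64.4% | 59.3% | 5.1 |
| 10%, 2.2 (19.4%) | 91.9% | 89.7% | 2.2 |

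CMH held its level under no effect (2.4 to 2.5%). Doubling the assumed stratum effects raises the loss in the first three rows to about 7 to 8 points.

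A second simulation used permuted blocks of 4, realised arm sizes, ISS effects of 0 to 0.8 log-odds per step, and Rd rates of 5 to 20%. The loss was 0.8 to 5.0 points when DRd is 5 to 8 percentage points higher (1.4 to 6.5 with exactly 365:365). At 15 percentage points it was at most 0.3 (0.4).

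**Effect measure.** At 10% v 20% the crude odds ratio is (0.20/0.80)/(0.10/0.90) = 2.25. Under the strongest ISS effect in the second simulation, the stratified odds ratio is 2.33. If ISS is not prognostic the two agree.

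**The case against.** The strongest reply is that nothing here is invalid. Fisher's test is prespecified and conservative, and protocol section 11 calls its own methods a general description: "Specific details will be provided in the Statistical Analysis Plan". A different test in the SAP is therefore allowed. That stands, and it rules out several stronger readings that a reader might infer:

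- **The documents leave two competing p-values.** They do not. Protocol section 11 defers to the SAP, and 4.3.3.2 names the test, the threshold and the population. Fisher is the identifiable formal test; only the reason is missing.
- **No MRD effect estimate is planned anywhere.** This goes too far. Protocol 11.3 plans the Mantel-Haenszel odds ratio for binary endpoints, and SAP 7.2.3 applies methods similar to those of 4.3.1.2 to MRD in an exploratory high-risk subgroup. What is missing is a between-arm estimate in 4.3.3.2 for the ITT analysis.
- **The SAP departs from its governing protocol.** This cannot be established. The SAP covers analyses "as specified in the protocol JNJ-54767414MMY3008, Amendment INT-4", and the supplied protocol is Amendment 9. Amendment 5 revised the secondary-endpoint text of 11.3. The log records no change of test, but the INT-4 wording is not available.
- **A conservative miss at step 3 could block overall survival.** The protocol reports that overall survival superiority was shown. If the SAP order was followed, MRD had already passed, and SAP 4.1.1 does not re-test a rejected hypothesis.

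The last point also means that the power loss may no longer matter for the formal test. The contrast with 4.3.1.2, which lies within the SAP itself, and the missing estimate do not depend on how large the effect was.

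**Conclusion.** The point holds as a minor one. Within a single SAP, one of four binary endpoints in the same hierarchy is tested without the randomisation strata and without a between-arm estimate, and no reason is given. Type I error is protected: Fisher's true size is about 1.5 to 1.9% against 2.44%, for assumed rates of 5 to 15%. The power loss against stratified CMH is roughly 5 to 6 points at small effects under moderate stratum effects, and negligible at large effects.

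These sizes rest on assumed MRD rates, stratum shares and prognostic strengths. The direction of the loss was the same in every scenario with power to lose. The inconsistency within the SAP and the absent ITT estimate rest on the text alone.

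**What to change.** **MRD analyses not yet run.** In SAP 4.3.3.2, use the stratified CMH test and the Mantel-Haenszel odds ratio with 95% interval from 4.3.1.2, and keep Fisher's exact test as a sensitivity analysis. The cost is SAP wording only, since the strata are already used for PFS and the response rates.

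**MRD analyses already run.** Keep Fisher as the formal result, because moving to a more powerful test after results are known would be post hoc. State why MRD was handled differently, and report the stratified CMH p-value and the Mantel-Haenszel odds ratio with 95% interval as supportive. The cost is one supplementary table and a sentence of rationale.

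**Separate clerical corrections in the SAP:**

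- 4.3.5.2 gives 360 PFS events for the primary PFS analysis; elsewhere the figure is 390.
- 4.3.8.2 refers sCR to 4.3.3.2, the Fisher section. It should refer to 4.3.1.2, which lists sCR under CMH.
- 7.1.2 refers MRD to 4.3.4, which is overall response and leads on to CMH. It should refer to 4.3.3.
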